## 5. Study Drug

### 5.1. Formulation

**5.1.1.** SYMTUZA (darunavir, cobicistat, emtricitabine, and tenofovir alafenamide) is an FDA approved fixed-dose combination tablet complete regimen for the treatment of HIV-1 infection in adults: • who have no prior antiretroviral treatment history or • who are virologically suppressed (HIV-1 RNA less than 50 copies per mL) on a stable antiretroviral regimen for at least 6 months and have no known substitutions associated with resistance to darunavir or tenofovir.. • Darunavir is an inhibitor of the HIV-1 protease. • Cobicistat is a mechanism-based inhibitor of cytochrome P450 (CYP) enzymes of the CYP3A family. • Emtricitabine, a synthetic nucleoside analog of cytidine, is an HIV nucleoside analog reverse transcriptase inhibitor (HIV NRTI). • Tenofovir alafenamide, an HIV NRTI, is converted in vivo to tenofovir, an acyclic nucleoside phosphonate (nucleotide) analog of adenosine 5'-monophosphate. SYMTUZA tablets are for oral administration. Each tablet contains darunavir ethanolate equivalent to 800 mg of darunavir, 150 mg of cobicistat, 200 mg of emtricitabine, and 11.2 mg of tenofovir alafenamide fumarate equivalent to 10 mg of tenofovir alafenamide. The tablets include the following inactive ingredients: colloidal silicon dioxide, croscarmellose sodium, magnesium stearate, and microcrystalline cellulose. The tablets are film-coated with a coating material containing polyethylene glycol (macrogol), polyvinyl alcohol (partially hydrolyzed), talc, titanium dioxide, and yellow ferric oxide.

**5.1.2.** Syntuza will be considered investigational in this study for those patients who are not virally suppressed at study entry.

### 5.2. Packaging and Labeling/Storage and Handling

**5.2.1.** SYMTUZA (darunavir, cobicistat, emtricitabine, and tenofovir alafenamide) tablets are supplied as yellow to yellowish-brown, capsule-shaped, film-coated tablets debossed with “8121” on one side and “JG” on the other side. SYMTUZA is packaged in bottles of 30 tablets (NDC 59676-800-30), with a silica gel desiccant and child-resistant closure.

**5.2.2.** Study drug will be stored at 20°C-25°C (between 68°F-77°F); with excursions permitted to 15°C-30°C (59°F-86°F). • Dispensed in the original container. Container will be tightly closed with desiccant inside to protect from moisture.

### 5.3. Dosage and Administration

**5.3.1.** Study drug will be dosed as one tablet taken orally once daily with food in adults. For subjects who are unable to swallow the whole tablet, it may be split into two pieces using a tablet-cutter, and the entire dose should be consumed immediately after splitting.

### 5.4. Concomitant Medications

#### 5.4.1. Contraindicated medications:

5.4.1.1. SYMTUZA® and the following drugs due to the potential for serious and/or life-threatening events or loss of therapeutic effect: alfuzosin, carbamazepine, cisapride, colchicine (in patients with renal and/or hepatic impairment), dronedarone, elbasvir/grazoprevir, ergot derivatives (such as: dihydroergotamine, ergotamine, methylergonovine), ivabradine, lomitapide, lovastatin, lurasidone, oral midazolam, naloxegol, phenobarbital, phenytoin, pimozide, ranolazine, rifampin, St. John’s wort (*Hypericum perforatum*), sildenafil for pulmonary arterial hypertension, simvastatin, and triazolam.

#### 5.4.2. Not recommended agents:

5.4.2.1. Rivaroxaban, escicabazepine, oxcarbazepine, voriconazole, rifapentine, rifabutin, betamethasone, budesonide, ciclesonide, dexamethasone, fluticasone, methylprednisolone, mometasone, triamcinolone, glecaprevir/pibrentasvir, simeprevir, everolimus, irinotecan, salmeterol, avanafil, ticagrelor.

**5.5. Accountability for Study Drug**

**5.5.1.** Subjects will be instructed to bring all study medication in the original container at each clinic visit for drug accountability. The Investigator will be responsible for maintaining accurate records for all study drug bottles dispensed and tablets returned. Study medication supplies, including partially used or empty bottles, must be accounted for by the investigator prior to destruction or return.

**5.5.2.** The Investigator is responsible for ensuring adequate accountability of all used and unused study drug. This included acknowledgement of receipt of each shipment of study drug (quality and condition). All used and unused study drug dispensed to subjects must be returned to the site.

**5.5.3.** Study Drug accountability records will include:

5.5.3.1. Date received and quantity of IMP kits

5.5.3.2. Date, subject number, subject initials, the IMP kit number dispensed

5.5.3.3. Date, quantity of used and unused IMP returned, along with the initials of the person recording the information.

**5.6. Product Return or Disposal**

**5.6.1.** Study drug return or disposal will be performed on site.

## 6. Study Design

### 6.1. Part 1

**6.1.1. Methodology**

6.1.1.1. Part I of the study is a Cohort Survey of HIV+ outpatient clinic patients currently receiving ART to assess medication adherence and tolerability.

**6.1.2. Sample**

6.1.2.1. Convenience sample of patients being seen in a single clinical site

6.1.2.2. Duration will be until enrollment of Part II has been completed

**6.1.3. Eligibility criteria****6.1.3.1. Inclusion Criteria:**

6.1.3.1.1. ≥ 18 years of age

6.1.3.1.2. HIV positive receiving ART of any type

**6.1.3.2. Exclusion criteria**

6.1.3.2.1. Inability to read/respond to questions written in English OR Spanish

**6.1.4. Study Procedure**

6.1.4.1. During patient triage, all patients who are HIV positive and currently prescribed anti-viral therapy will be offered participation in completing the Midland ART Adherence Survey (MAAS, Appendix 1). They will be provided a paper copy of the Study consent and the survey with a clipboard and a pen and allowed to self-complete it during the triage process. If they opt-in to the survey, they will turn in the completed surveys to staff members who will (1) determine if patient is eligible for Part II of study and (2) share the results with the provider, if subjects indicate they would like them shared. For those who opt out, no demographic data will be collected.

6.1.4.2. Survey sheets will not contain any Personal Identifying Information (PII). The results of the survey will be entered into a spreadsheet and analyzed at the completion of the enrollment period.

6.1.4.3. Subjects will be offered enrollment in Part 1 until target enrollment in part 2 has been completed or until subject sample population has been offered participation, whichever comes first.

## 6.2. Part 2

### 6.2.1. Methodology

6.2.1.1. Part 2 of the study is a prospective cohort analysis of change in adherence, tolerability and safety of subjects who reports poor adherence to ART due to intolerance/side effects from integrase inhibitor containing regimens when they are switched to DRV/COB/FTC/TAF and monitored for 4 months.

### 6.2.2. Sample

6.2.2.1. All subjects who meet pre-determined criteria from MAAS and meet other eligibility requirements will be offered enrollment into Part II of the study, the target enrollment is 30.

### 6.2.3. Eligibility Criteria

#### 6.2.3.1. Inclusion Criteria

6.2.3.1.1. Meets inclusion criteria of part I of study

6.2.3.1.1.1. Currently on an integrase containing regimen AND

6.2.3.1.1.2. Reports non-adherent due to medication intolerance, defined by pre-determined criteria from Adherence Survey: [indicate a side effect to question 11 OR "yes" to questions 3 OR 7] AND [indicate missing more than 2 doses per month on question 8 OR 9 OR 10]

6.2.3.1.2. GFR $\geq$ 30mL/min

6.2.3.1.3. AST/ALT  $\leq$  3 times upper limit of normal

6.2.3.1.4. Total bilirubin of  $\leq$ 1.5 mg/dL

#### 6.2.3.2. Exclusion Criteria

6.2.3.2.1. Known resistance to darunavir or tenofovir

6.2.3.2.2. Known intolerance to Syntuza or its components

6.2.3.2.3. Current pregnancy

6.2.3.2.4. Requires continued use of any of the agents in table 6.2.3.2.4

6.2.3.2.5. Cirrhosis, regardless of compensation status

6.2.3.2.6. Active, serious infections within 30 days of baseline

6.2.3.2.7. History of malignancy within 5 years of baseline, except cutaneous Kaposi's sarcoma, basal cell or resected non-invasive cutaneous squamous cell carcinoma

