6.2.3.2.8. Life expectancy of less than a year

6.2.3.2.9. Participation in any other investigation study 30 days prior to enrollment

Table 6.2.3.2.4 Contraindicated/not recommended Concomitant Medications

Alpha 1-Adrenoreceptor Antagonist	alfuzosin
Antiarrhythmics/Antianginals	amiodarone, dronedarone, ivabradine, lidocaine (systemic)
Anti-coagulants	apixaban, rivaroxaban,
Anti-convulsants	carbamazepine, phenobarbital, phenytoin, oxcarbazepine, eslicarbazepine
Anti-gout	colchicine (in patients with renal and/or hepatic impairment)
Antimycobacterial	Rifampin, rifapentine, rifabutin
Ergot Derivatives	Such as: dihydroergotamine, ergonovine, ergotamine
Hepatitis C Virus Direct-Acting Antivirals	elbasvir/grazoprevir, glecaprevir/pibrentasvir, simeprevir
Herbal Products St.	John's wort (Hypericum perforatum)
HMG-CoA Reductase Inhibitors	lovastatin, simvastatin
Other Lipid Modifying Agents	lomitapide
Inhaled Beta Agonist	salmeterol
Neuroleptics	lurasidone, pimozide
Opioid Antagonist	naloxegol
PDE-5 Inhibitor	sildenafil (for treatment of pulmonary arterial hypertension), avanafil
Platelet Aggregation Inhibitor	ticagrelor
Sedatives/Hypnotics	triazolam
Antiplatelet	ticagrelor
antineoplastic	Everolimus, irinotecan
antifungals	voriconazole
Steroids	betamethasone, budesonide, ciclesonide, dexamethasone, fluticasone, methylprednisolone, mometasone, triamcinolone

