##### 6.2.4.3. Screening Visit

6.2.4.3.1. At screening, written informed consent will be obtained; medical history of HIV-1 disease, current medications and medication history will be documented, any available HIV-1 resistance assays and hepatitis B immunity/viral loads will be documented, vitals (blood pressure, pulse, temperature, height and weight) from triage will be documented, physical exam will be performed.

6.2.4.3.2. After screening is performed, subjects will be allowed to either initiate baseline assessment or return within 45 days to do so.

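### The exclusion list of concomitant drugs leaves out three drugs that section 5.4.1 contraindicates: cisapride, oral midazolam and ranolazine

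*Protocol*

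**What the plan says.** Three places in the Protocol deal with drugs that may not, or should not, be taken with study drug.

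- **Section 5.4.1** gives the contraindicated drugs. Its reason covers the whole list: "SYMTUZA® and the following drugs due to the potential for serious and/or life-threatening events or loss of therapeutic effect". It does not say which reason belongs to which drug. The list includes "alfuzosin, carbamazepine, cisapride, colchicine (in patients with renal and/or hepatic impairment") and, further on, "oral midazolam, naloxegol, phenobarbital, phenytoin, pimozide, ranolazine, rifampin".
- **Section 5.4.2** gives a second list of drugs that are only advised against, beginning "Rivaroxaban, escicabazepine, oxcarbazepine, voriconazole, rifapentine, rifabutin, betamethasone, budesonide, ciclesonide".
- **Exclusion criterion 6.2.3.2.4** shuts out a subject who "Requires continued use of any of the agents in table 6.2.3.2.4". The table it points to is titled "Contraindicated/not recommended Concomitant Medications", so by its title it should hold both lists from section 5.4. Appendix 6 repeats the table's content.

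At the screening visit (6.2.4.3), "current medications and medication history will be documented". No step there directs staff to compare that record with section 5.4.1.

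**The concern.** An exclusion criterion that works through a list is only as good as the list. Here the title promises both tiers of section 5.4, yet three drugs from the contraindicated tier are absent. The criterion does not cite section 5.4.1, so nothing in the eligibility section makes up for the gap. Section 6.2.2.1 says that everyone who meets the survey criteria and the other eligibility requirements is to be offered enrolment. Read literally, a subject who needs ranolazine, for example, is eligible and is to be offered a drug that section 5.4.1 says must not be given with it.

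What is at stake is subject safety, not the primary analysis. Two sections of one protocol give different answers on whether such a subject may enter, and the section that staff use to decide eligibility gives the unsafe answer. Section 9.10.1 has the inclusion/exclusion form completed from eligibility data. A form built from 6.2.3 would not flag these drugs, and checking Appendix 6 would not help.

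**Working it through.** There is no plan figure to reproduce. The check compares the lists entry by entry.

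**Inputs.** The contraindicated list (5.4.1.1), the not-recommended list (5.4.2.1), Table 6.2.3.2.4 and Appendix 6. Counting rules:

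- A fixed combination counts as one entry.
- Ergot derivatives count as one entry. Methylergonovine is named in 5.4.1 and not in the table, but the table's ergot row is open-ended, so this is not counted as an omission.
- Ticagrelor appears in two rows of the table and is counted once.
- Spelling variants of eslicarbazepine and carbamazepine are treated as matches.

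**Step 1: coverage of each section 5.4 list.**

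| Source list | Entries | In Table 6.2.3.2.4 | In Appendix 6 | Missing from both |
|---|---|---|---|---|
| 5.4.1 contraindicated | 22 | 19 | 19 | cisapride, oral midazolam, ranolazine |
| 5.4.2 not recommended | 21 | 21 | 21 | none |

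Share of the contraindicated list that is missing: 3 / 22 = 13.6%. This is a share of list entries, not of subjects or of risk.

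**Step 2: reconcile the table's total.** The table names 43 distinct drugs or classes: 19 (from 5.4.1) + 21 (from 5.4.2) + 3 found only in the table (amiodarone, systemic lidocaine, apixaban) = 43. Appendix 6 names the same 43. Every entry is accounted for, so the three missing drugs are not listed under another heading.

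**Step 3: could text have been lost in the PDF?** This is unlikely. The antiarrhythmic/antianginal row, where ranolazine would belong, reads "amiodarone, dronedarone, ivabradine, lidocaine (systemic") in both the table and the appendix. The sedative/hypnotic row, where midazolam would belong, holds triazolam alone in both. Neither list has a row that would take cisapride. Two separate tables lack the same three drugs, and the rows where two of them would sit are intact.

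**Step 4: does another criterion catch them?** The remaining criteria in 6.2.3 concern:

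- age, receipt of ART, language, an integrase-containing regimen and the survey answers;
- renal function, liver enzymes and bilirubin;
- resistance, known intolerance and pregnancy;
- cirrhosis, serious infection, malignancy and life expectancy;
- participation in other studies.

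None refers to cisapride, midazolam or ranolazine, or to section 5.4.

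**Step 5: effect of the correction.** Adding the three names raises coverage of section 5.4.1 from 19 of 22 to 22 of 22.

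**The case against.** The strongest reply is that the protocol is not silent. Section 5.4.1 names all three drugs as contraindicated, so co-administration is not permitted anywhere. Several safeguards stand behind that:

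- medications are recorded at screening;
- the investigator must run the study according to the protocol and protect subjects (9.2.1, 9.12.1);
- a qualified person makes the medical decisions (9.4.1);
- there is one site, so no second team has to interpret the two lists.

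On this view the fault is a transcription slip between two lists. Actual harm is conjecture, and the criterion in any case applies only to subjects who cannot stop the drug.

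Much of this is fair. The slip does not authorise co-administration, and a careful clinician could well catch it. The number affected is unknown and may be zero. The discontinuation rules in section 7.7 do not mention use of any contraindicated drug, including the 19 that are in the table, so their silence says nothing special about these three.

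The rest does not remove the point. The duties listed are general, and the screening step records medications without directing a check against section 5.4.1. They narrow the gap but do not close it. An eligibility rule should give the right answer when it is followed as written, and this one does not.

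**Conclusion.** The concern holds. Table 6.2.3.2.4 and Appendix 6 each omit 3 of the 22 contraindicated entries in section 5.4.1, and the only eligibility criterion on concomitant drugs relies on that table. The omission looks like an oversight: the title covers both tiers, the not-recommended tier is complete, the table even goes beyond section 5.4 with three additional drugs, and no reason is given for leaving these three out.

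This is an internal inconsistency in a safety criterion and should be corrected before enrolment relies on it. That judgement rests on the seriousness of the hazard as section 5.4.1 itself states it, not on expected frequency. The number of the 30 target subjects who might need one of these drugs cannot be derived from the documents. The conclusion assumes that the table is printed in full, which the matching gap in Appendix 6 supports.

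**What to change.** Add cisapride, oral midazolam and ranolazine to Table 6.2.3.2.4 and to Appendix 6. Alternatively, reword criterion 6.2.3.2.4 so that it excludes subjects who need continued treatment with any drug in the table or in section 5.4.1. The second form also guards against later drift between the lists. The eligibility form should be updated to match.

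A minor point of harmonisation: amiodarone, systemic lidocaine and apixaban are excluded by the table but not named in section 5.4. An exclusion list may be broader, so this is not an error. If their exclusion is intended, section 5.4 could name them too.

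The cost is a wording amendment to one table and one appendix, or to one criterion, with the usual IRB approval under 9.14.1. Sample size, visits and analysis do not change.

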6.2.3.2.8. Life expectancy of less than a year

6.2.3.2.9. Participation in any other investigation study 30 days prior to enrollment

Table 6.2.3.2.4 Contraindicated/not recommended Concomitant Medications

Alpha 1-Adrenoreceptor Antagonist	alfuzosin
Antiarrhythmics/Antianginals	amiodarone, dronedarone, ivabradine, lidocaine (systemic)
Anti-coagulants	apixaban, rivaroxaban,
Anti-convulsants	carbamazepine, phenobarbital, phenytoin, oxcarbazepine, eslicarbazepine
Anti-gout	colchicine (in patients with renal and/or hepatic impairment)
Antimycobacterial	Rifampin, rifapentine, rifabutin
Ergot Derivatives	Such as: dihydroergotamine, ergonovine, ergotamine
Hepatitis C Virus Direct-Acting Antivirals	elbasvir/grazoprevir, glecaprevir/pibrentasvir, simeprevir
Herbal Products St.	John's wort (Hypericum perforatum)
HMG-CoA Reductase Inhibitors	lovastatin, simvastatin
Other Lipid Modifying Agents	lomitapide
Inhaled Beta Agonist	salmeterol
Neuroleptics	lurasidone, pimozide
Opioid Antagonist	naloxegol
PDE-5 Inhibitor	sildenafil (for treatment of pulmonary arterial hypertension), avanafil
Platelet Aggregation Inhibitor	ticagrelor
Sedatives/Hypnotics	triazolam
Antiplatelet	ticagrelor
antineoplastic	Everolimus, irinotecan
antifungals	voriconazole
Steroids	betamethasone, budesonide, ciclesonide, dexamethasone, fluticasone, methylprednisolone, mometasone, triamcinolone

#### 6.2.4. Study Procedure

##### 6.2.4.1. Overview

6.2.4.1.1. Subjects who are referred for screening from Part I who meet other eligibility criteria (see table 6.2.4.2.1) will be offered enrollment in Part 2. Those who provide consent will complete HIV Symptom Index (HIV-SI), a validated Patient Reported Outcome survey to assess side effects/quality of life, undergo physical and laboratory examinations, and ART will be switched to DRV/COB/FTC/TAF (Syntuza). For subjects who were not suppressed at their last lab evaluation, an HIV genotype will be performed prior to enrollment. Subjects who do not provide consent to enroll in the study will be referred back to their provider to address issues with tolerance and adherence.

6.2.4.1.2. Subjects will be followed for 16 weeks. During that period, they will be brought back for evaluation at the 4th and 16th week. At those evaluations, they will again complete the PRO and adherence surveys to assess tolerability and adherence. At the evaluations, they will also be monitored for safety and effectiveness via physical exams and laboratory studies. See Table 6.2.4.1.2

6.2.4.1.2.1. Labs at each visit: Complete Blood Count, Complete Metabolic Panel, Urinalysis, CD4 panel, HIV1 Quantitative viral load. If subject is of childbearing potential, urine pregnancy will be performed.

6.2.4.1.2.1.1. Special situations: If HIV viral load is >200 prior to baseline and not accompanied by recent genotype, a genotype will be performed.

6.2.4.1.3. Interim analysis will be performed when all subjects have completed 1 month evaluation or when 10 subjects have completed 4 month evaluation, whichever comes first.

##### 6.2.4.2. Positive Screen

6.2.4.2.1. Subjects who screen positive from adherence survey defined as: (1) (indicate "yes" to questions 3 OR 7; or indicate a side effect to question 11) AND (2) (indicate missing more than 2 doses per month on question 8 OR 9 OR 10) will be offered enrollment in Part II.

Table 6.2.4.2.1 Positive Screen for Part 2

Positive screen for Part II one positive response in both columns:	
One from below	One from below
Question 3 = "Yes"	Question 8 = not "always" or "almost always"
Question 7 = "Yes"	Question 9 = greater than 2
Question 11 = "Side effect(s)" or named side effect	Question 10 = greater than 2

##### 6.2.4.3. Screening Visit

6.2.4.3.1. At screening, written informed consent will be obtained; medical history of HIV-1 disease, current medications and medication history will be documented, any available HIV-1 resistance assays and hepatitis B immunity/viral loads will be documented, vitals (blood pressure, pulse, temperature, height and weight) from triage will be documented, physical exam will be performed.

6.2.4.3.2. After screening is performed, subjects will be allowed to either initiate baseline assessment or return within 45 days to do so.

**6.2.4.4. Baseline Visit**

- 6.2.4.4.1. If required labs have been performed within 30 days baseline may be performed same day and self-completed HIV Symptom Index (HIV-SI, Appendix 2) survey will be completed, baseline labs will be drawn and patient will be given 30 day supply of study drug.
- 6.2.4.4.2. If baseline is not done same day: vitals will be taken prior to HIV-SI survey being completed. Then updated history and symptom based physical will be performed and baseline labs will be drawn. Patient will be given 30 day supply of study drug; first dose will be taken in office.

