**6.2.4.9. Post Study Visit**

- 6.2.4.9.1. If any significant abnormality is detected either at 4 month end of study visit or early discontinuation visit, a repeat exam and laboratories will be performed approximately 30 days following (or sooner, if PI believes to be clinically indicated) to ensure their resolution, unless at the determination of the PI they are deemed not related to the study drug.

Table 6.2.4.1.2: Overview of Study Procedures

Procedures	Screening and/or Baseline Combined Visit	Screening (if not same day as screen)	Baseline (if not same day as screen)	Week 4	Week 14 Event	Week 16	Early Discontinuation
Vitals	X	X	X	X		X	X
MAAS	X	X		X		X	X
HIV-SI	X		X	X		X	X
History and Physical	X	X					
History and Symptom based physical			X	X		X	X
Complete Blood Count	X		X	X		X	X
CD4 panel	X		X	X		X	X
Complete Metabolic Panel	X		X	X		X	X
HIV-1 Quantitative viral load	X		X	X		X	X
Urinalysis	X		X	X		X	X
Study Drug Dispensation			X	X			
Treatment Adherence and Accountability				X		X	
Commercial Script sent to Patient's Pharmacy					X		
HIV Genotype	if viral load >200 copies/mL at last check		if viral load >200 copies/mL at last check	if viral load >200 copies/mL at last check		if viral load >200 copies/mL at last check	if viral load >200 copies/mL at last check
Urine pregnancy	if indicated		if indicated	if indicated		if indicated	if indicated
Hepatitis B viral load	if indicated		if indicated	if indicated		if indicated	if indicated

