#### **9.10. Case Report Forms**

- 9.10.1.** For each subject consented, a study file will be completed by an authorized study staff member who has completed training for this function. The study file will only capture the data required per the protocol schedule of events and procedures. The Inclusion/Exclusion Criteria and Enrollment should be completed only after all data related to eligibility have been received. Subsequent to data entry, a second staff member will perform source data verification.

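### On the separate-baseline path, the protocol does not provide for the renal and hepatic eligibility criteria to be checked before the first dose

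*Protocol*

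**What the plan says.** **Criteria.** Section 6.2.3.1 sets three inclusion limits that need a laboratory result: GFR of at least 30 mL/min, AST/ALT of at most 3 times the upper limit of normal, and total bilirubin of at most 1.5 mg/dL. Section 6.2.3.2.3 excludes current pregnancy.

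**Screening.** Section 6.2.4.3.1 lists consent, history, medications, available resistance and hepatitis B data, vitals and a physical examination. It lists no blood or urine test. Section 6.2.4.3.2 then lets the subject start baseline at once or come back within 45 days.

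**Same-day baseline (6.2.4.4.1).** This path is conditional: "If required labs have been performed within 30 days baseline may be performed same day".

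**Separate baseline (6.2.4.4.2).** After vitals, the symptom survey, an updated history and a physical, "baseline labs will be drawn. Patient will be given 30 day supply of study drug; first dose will be taken in office". No prior-laboratory condition appears.

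**Schedules.** In Table 6.2.4.1.2 and in Appendix 5, the separate Screening column (its label begins "Screening (if not same day as screen") is blank for the metabolic panel and for urine pregnancy. On this path both first appear at Baseline.

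**Eligibility data.** Section 9.10.1, under Case Report Forms, says the inclusion/exclusion and enrolment items "should be completed only after all data related to eligibility have been received".

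**The concern.** A criterion that rests on a laboratory value can only screen subjects if the value is in hand before treatment starts. On the separate path, the only chemistry result the protocol arranges for is drawn at the visit where treatment starts. The condition on recent laboratory work is attached to the same-day path. It is absent from the path that a subject without such results has to take.

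What is at stake is mainly participant safety: exposure of someone whom the protocol's own limits would have kept out. There is also a data consequence. Such a subject, once enrolled and dosed, belongs to both the intent-to-treat set (all enrolled, 8.3.3) and the modified set (one dose taken, 8.3.4), and the protocol would have on record an ineligible subject whom its own visit sequence admitted.

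**Working it through.** No figure in the protocol bears on this point, so the check sets the sections side by side. One assumption is needed. The protocol does not say which test supplies GFR, AST/ALT and bilirubin; I take it to be the metabolic panel, the only chemistry test on the schedules.

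| Step | Same-day path | Separate path |
|---|---|---|
| Prior results required? | Yes, within 30 days (6.2.4.4.1) | None stated (6.2.4.4.2) |
| Metabolic panel at Screening? | Yes, at the combined visit | No (6.2.4.3.1, Table 6.2.4.1.2, Appendix 5) |
| First scheduled panel | Combined visit | Baseline |
| Drug dispensed | That visit | Baseline |
| Wait for the new result before dosing? | Not stated, but earlier results are required | Not stated; first dose taken in the office |

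1. *Is a renal or hepatic result guaranteed before the first dose?* On the same-day path, yes, through the 30-day condition. On the separate path, no: nothing is scheduled earlier, no earlier result is required, and draw and dose share a visit.

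2. *Could the panel be read before the in-office dose?* No turnaround is stated. Section 7.6.5.2.1, on ALT flare, has the subject called back once results are received, ideally within 3 days of the draw. That suggests panel results normally arrive after the visit.

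3. *Does the overview supply a screening draw?* Section 6.2.4.1.2.1 lists laboratory tests for each visit, but it sits beneath the paragraph on the Week 4 and Week 16 evaluations. If it were meant to reach the separate Screening visit, it would contradict both schedules, so reconciliation would still be needed.

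4. *How old could existing results be?* The separate path sets no limit. Suppose, as an assumption, that the 30-day window were applied at screening. With the 45-day return, the oldest admissible result at first dose would be 30 + 45 = 75 days. The protocol does not state even that limit.

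5. *Pregnancy.* The test is a urine test for subjects of childbearing potential (6.2.4.1.2.1), listed as needed at the separate Baseline. It can be done and read at that visit before the dose. The text does not say that it must be.

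**The case against.** The strongest reply is that the criteria still bind. Part 2 is offered only to those who meet the eligibility requirements (6.2.2.1, 6.2.4.1.1). Subjects are existing clinic patients on treatment, and 6.2.4.1.1 refers to their last laboratory evaluation, so routine-care results may well exist. Nothing forbids using them. This stands, and it is why a reader who inferred that the criteria *cannot* be applied before dosing would go too far. What remains is that 6.2.4.4.2 neither requires such results nor limits their age.

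A second reply concerns 9.10.1. It sits under Case Report Forms. If it governs only when a form is filled in, it does not strictly collide with 6.2.4.4.2. If it gates enrolment, it already forbids dosing a subject whose results are pending, and 6.2.4.4.2 must be read subject to it. This also stands in part: the conflict is between an unclear visit sequence and a general rule, and the protocol does not direct staff to dose ineligible subjects. Site staff following the visit text and the schedules would nevertheless meet no step that applies the rule.

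Three further inferences are tempting but unsupported:

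- *That everyone on this path lacks recent results.* Section 6.2.4.3.2 lets subjects simply return later, so some will have them.
- *That the blood count and viral load missing from Screening matter equally.* Neither is an eligibility limit.
- *That the primary endpoint is biased.* With 30 subjects, one subject is 1/30 = 3.3 percentage points. The proportion moves by that amount only if the subject's adherence classification differs, and nothing in the protocol ties renal or hepatic values to the adherence score. Nor does any section score discontinuation as suboptimal adherence; 6.2.4.8 and 7.7.3 try to keep such subjects in follow-up to Week 16.

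**Conclusion.** The point holds for the renal and hepatic criteria. On the separate-baseline path, the protocol schedules no metabolic panel before the dosing visit, requires no prior result and sets no wait for the new one. This is out of step with its own same-day path and in tension with 9.10.1. For pregnancy, only the order of test and dose is left open.

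The size cannot be given: the protocol does not say how many subjects will use the separate path or how many of those will lack usable results. The conclusion assumes that the metabolic panel supplies the three values and that its results usually arrive after the visit. If results were available on the spot, the gap would shrink to an unfixed order, as with pregnancy. The case for correction rests on participant safety and on agreement between sections. No effect on the primary analysis is claimed.

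**What to change.** Reconcile 6.2.3.1.2 to 6.2.3.1.4, 6.2.4.3.1, 6.2.4.4.1, 6.2.4.4.2, Table 6.2.4.1.2, Appendix 5 and 9.10.1, so that the visit sequence and both schedules agree with the eligibility criteria and with the rule on eligibility data. State also how the urine pregnancy test and the first dose are ordered at the separate Baseline visit, and whether the list of tests in 6.2.4.1.2.1 covers Screening. How the sequence is arranged is for the sponsor to decide; no clinical rule is proposed here.

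The cost is a protocol amendment to wording and schedule marks. Depending on the sponsor's choice, the timing of a draw or of the first dose may change for some subjects. The sample size and the analysis are unaffected.
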